Official Title: Foot progression angle modification: an exploratory six-week intervention in people with knee osteoarthritis.

NCT Number: TBD

Document Date: March 24th, 2020

Study Protocol

Study Design

This parallel-group randomized clinical trial will consist of a 6-week gait modification intervention, delivered to two groups of older adults with medial compartment knee osteoarthritis (OA). The first group will receive a conventional delivery of gait modification (group name: SMOD), whereby they will practice the gait modification with a specific target (rotate foot 15° inward or outward relative to baseline). The second group will self-select the amount of modification they perform (group name: AMAC), guided by the instruction to “change foot rotation as much as is comfortable”. Foot rotation (toe-in or toe-out walking) is measured during the stance phase of walking as the angle of the foot’s long axis (heel to toe) relative to the direction of walking, and termed foot progression angle (FPA). In-lab and real-world gait analysis will be used to examine how the modification is learned, as well as the effect of the modification on biomechanical and clinical outcomes relevant to knee OA. In-lab assessment will be performed at baseline and a 7 week follow-up, while real-world assessment will be performed during the intervening weeks using wearable sensor technology (a custom sensorized shoe design). Both within-group and between-group comparisons will be made to identify differences in learning, difficulty, biomechanical, and clinical outcomes.

Primary Hypotheses

- H1: Participants receiving the specific FPA target will exhibit improved learning outcomes (e.g. lower error in performance, higher proportion of steps with $\geq 7^\circ$ of change from baseline FPA and lower variability) from week 1 to week 6, as measured during gait modification practice sessions, learning assessments, and during daily walking activity.
- H2: Participants receiving the self-directed FPA modification will exhibit improved learning outcomes (higher proportion of steps with $\geq 7^\circ$ of change from baseline FPA and lower variability) from week 1 to week 6, as measured during gait modification practice sessions, learning assessments, and during daily walking activity.
- H3: We expect FPA variability will be larger in the self-directed group, but both groups will exhibit a similar proportion of steps with $> 7^\circ$ of change from baseline FPA.

Secondary Hypotheses

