- H4: Those in the self-directed modification group will exhibit smaller average changes in FPA compared to those in the conventional gait modification group. However, those in the self-directed modification group will report lower ratings of difficulty in performing the modification, compared to the specific-target gait modification group.
- H5: Both groups will exhibit improvements in biomechanical (e.g. knee adduction moment) and clinical outcomes (e.g. knee pain, physical function) at follow-up, compared to baseline.
- H6: Biomechanical (e.g. knee adduction moment) and clinical outcome (e.g. knee pain, physical function) change scores from baseline to follow up will not differ between groups.

Participants

Adults with knee OA will be recruited and randomized into two treatment arms. All eligible

participants will: 1) be 50 years of age or greater, 2) exhibit signs of tibiofemoral OA (a score of ≥ 2 on the Kellgren and Lawrence (KL) grading scale [1]) predominantly in the medial compartment, 3) self-reported knee pain $\geq 3 / 10$ on a numerical rating scale of pain (NRS; 0 = “no pain” and 10 = “worst pain imaginable”) during most days of the previous month, 4) are comfortable walking intermittently for 30 minutes, and 5) fit into the available sizes of sensorized shoes (sizes spanning US women’s 5 to men’s 13).

Exclusion criteria include: 1) any knee surgery or intraarticular injections within the past 6 months, 2) a history of joint replacement surgery or high tibial osteotomy, 3) current or recent (within 6 weeks) corticosteroid injections, 4) use of a gait aid, 5) currently on a wait list for joint replacement surgery or high tibial osteotomy, 6) any inflammatory arthritic condition, 7) any other conditions that may affect normal gait or participation in an aerobic exercise program, and 8) cannot attend all required appointments at UBC. Additionally, potential participants will undergo an initial gait screening similar to a recent study [2] (details are outlined below), with the goal of identifying participants who are capable of reducing their KAM magnitude when FPA is modified. This gait screen will examine both natural walking FPA and changes in knee load while walking with increased toe-in and toe-out. Those who do not elicit a reduction in KAM impulse $\geq 5\%$ when FPA is changed by 10° in either direction will be excluded from the study as they would be considered non-responders.

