directly in front of the treadmill. The SMOD group will be guided to increase their FPA by 15° in either the toe-in or toe-out direction (determined by the gait screen). A line of tape will be aligned on the mirror according to the target FPA, as we have done previously [5, 17]. This mirror-based method of providing a target for the FPA modification was shown to be similarly effective when compared to feedback delivered using an expensive real-time motion capture system, but with significantly greater clinical feasibility. The AMAC group will be instructed to increase their FPA by “as much as is comfortable”. The mirror will be provided during practice sessions; however, no tapeline will be placed. The amount of time spent with the feedback (mirror) visible will be progressively reduced (faded feedback) across the six weekly practice sessions in order to reduce the reliance on feedback [18]. Before and immediately after the practice sessions, the participant will perform a warm-up and cool-down walk while wearing the sensorized shoes (10-minute outdoor standardized walking loop). This will provide a repeatable non-laboratory-based measure of FPA. Both groups will be encouraged to practice their gait modification at any opportunity during their daily at-home walking. Practice sessions will be led by a kinesiologist with experience delivering gait modification interventions.

Learning will be measured during 1) practice, 2) immediate and delayed retention tests, 3) dual-task tests, 4) transfer tests, and 5) during at-home/community walking. Each test (2-4) will last 1 min and be collected at each practice session. For the SMOD group, the absolute performance error (absolute error = |performed FPA – target FPA|), FPA variability, and the proportion of steps with >7° of change from baseline FPA will be measured using the sensorized shoe. For the AMAC group, FPA variability and the proportion of steps with >7° of change from baseline FPA will be measured. Retention tests will occur immediately before (starting at practice session 2) and after practice bouts. The participant will be asked to perform their gait modification as accurately as possible for 1 minute. Dual-task testing will be performed identically to the baseline assessment described above; however, the participant will be asked to simultaneously perform their gait modification. Lastly, transfer testing will be performed during stair ascent and descent in the same manner as the baseline assessment.

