Official Title: Foot progression angle modification: an exploratory six-week intervention in people with knee osteoarthritis.

NCT Number: TBD

Document Date: Mar 24th, 2020

Statistical Analysis Plan

Statistical analyses will be performed by an independent statistician. Means and standard deviations will be calculated for each outcome measure and baseline demographic characteristic. Baseline demographic data (e.g. age, body mass index, disease severity) will be examined for between-group differences using unpaired two-tailed t-tests. For all statistical analyses, alpha will be set to 0.05. Any multiple pairwise comparisons will be adjusted using the Bonferroni correction method.

Data will be assessed for sphericity, homoscedasticity, and normality using Mauchley's test, residual versus predicted plots, and quantile-quantile plots. Homoscedasticity and normality assumptions will be confirmed using Levene's test and Shapiro-Wilk's test, respectively. Sphericity assumption violations will be corrected for using the Greenhouse Geisser approach. Violations of homoscedasticity will be corrected for by bootstrapped model parameters. If normality is not met, a non-parametric test will be used.

Primary Hypotheses:

Repeated measures analyses of variance (ANOVA) will be performed to examine the within-group changes in learning outcomes over the six-week intervention. Between-group differences will be examined using a two-way mixed ANOVA, with the repeated measure being the learning outcome (foot progression angle change from baseline during in-lab and at-home walking) and the between-subject factor being group assignment (SMOD vs AMAC).

Secondary Hypotheses:

Biomechanical (knee joint moments), clinical (NRS knee pain, KOOS pain, symptoms, and physical function scores), and difficulty (difficulty of performing the FPA modification) change scores will be examined using an analysis of covariance (ANCOVA) with significant between-group baseline demographic group differences and baseline outcome values included as covariates.

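### The SAP's only primary between-group model analyses FPA change from baseline, the variable of secondary H4, and leaves primary H3's outcomes (FPA variability and proportion of steps beyond 7°) without a named test

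*SAP*

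**What the plan says.** H3, under Primary Hypotheses in the protocol, is the only primary hypothesis that compares the arms: "We expect FPA variability will be larger in the self-directed group, but both groups will exhibit a similar proportion of steps with" more than 7° of change from baseline. H1 and H2 are within-arm. H2 shows what the protocol means by learning outcomes: "Participants receiving the self-directed FPA modification will exhibit improved learning outcomes (higher proportion of steps with" at least 7° of change, together with lower variability.

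The protocol's section on the gait modification intervention lists the learning measures. SMOD has absolute error, variability and the step proportion. AMAC has the last two: "For the AMAC group, FPA variability and the proportion of steps with" more than 7° of change.

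The SAP's Primary Hypotheses section contains two analyses:
- a within-group one: "Repeated measures analyses of variance (ANOVA) will be performed to examine the within-group changes in learning outcomes over the six-week intervention"
- a between-group one, a two-way mixed ANOVA with SMOD versus AMAC as the between-subject factor, "with the repeated measure being the learning outcome (foot progression angle change from baseline during in-lab and at-home walking").

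H4, under Secondary Hypotheses in the protocol, reads: "Those in the self-directed modification group will exhibit smaller average changes in FPA compared to those in the conventional gait modification group". The SAP's secondary analysis covers biomechanical and clinical scores "and difficulty (difficulty of performing the FPA modification) change scores will be examined using an analysis of covariance (ANCOVA").

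**The concern.** A primary hypothesis should map to a model whose dependent variable is the quantity in the hypothesis. Here the primary between-group model takes the variable of a secondary hypothesis, and H3's two outcomes have no between-group model.

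Two things follow if the SAP is applied literally. A result for H4 would be reported as the primary between-arm finding. Any analysis of H3 would then have to be chosen later, including which of the several settings (practice, retention, dual-task, transfer, daily walking) and which weeks to use. Variability is the outcome on which H3 predicts that the arms differ, so its absence matters most.

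**Working it through.** **Matching hypotheses to models**

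| Hypothesis | Comparison | Outcome in the protocol | Between-group model in the SAP |
|---|---|---|---|
| H3 (primary) | SMOD v AMAC | FPA variability | none named |
| H3 (primary) | SMOD v AMAC | proportion of steps beyond 7° | none named |
| H4 (secondary) | SMOD v AMAC | average FPA change | mixed ANOVA, listed as primary |
| H4 (secondary) | SMOD v AMAC | difficulty | ANCOVA |
| H6 (secondary) | SMOD v AMAC | biomechanical and clinical change | ANCOVA |

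The SAP's within-group sentence speaks of learning outcomes in the plural. The between-group sentence that follows speaks of one learning outcome and says in parentheses what it is. FPA change does not appear in H2's list or in the protocol's list of learning measures.

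**Can FPA change stand in for H3's outcomes?**

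The documents give no step-level means or SDs, so those below are assumptions, with steps taken as normal. Change is measured in the intended direction.

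Share of steps beyond 7° = 1 − Φ((7 − mean)/SD).

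Same mean change, different variability:
- mean 12°, SD 3°: 1 − Φ(−1.667) = 0.952
- mean 12°, SD 5°: 1 − Φ(−1.000) = 0.841

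So two arms with no difference in mean change could differ by 11 points in the step proportion (95% v 84%).

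Same 2° difference in mean change, in the direction H4 predicts:

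| SMOD mean/SD | AMAC mean/SD | SMOD share | AMAC share | Gap |
|---|---|---|---|---|
| 15/3 | 13/3 | 0.996 | 0.977 | 0.019 |
| 10/3 | 8/3 | 0.841 | 0.631 | 0.211 |
| 15/3 | 13/5 | 0.996 | 0.885 | 0.111 |
| 10/3 | 8/5 | 0.841 | 0.579 | 0.262 |

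The last two rows give AMAC the larger variability that H3 expects. One and the same result on FPA change is compatible with nearly equal step proportions or with a gap of 26 points, and it says nothing about variability itself.

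**Precision available for H3**

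The Participants section of the protocol gives 30 required and 36 recruited in total, so 15 or 18 per arm. The unadjusted 95% CI half-width for a two-group difference, in SD units, is t(0.975, 2n − 2) × √(2/n):
- n = 15: 2.048 × 0.365 = 0.748
- n = 18: 2.032 × 0.333 = 0.677

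**Power for the group effect**

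The protocol sized the group × measure interaction with f = 0.175, 4 measures and N = 30. The correlation ρ between measures is not stated, so 0.5 to 0.7 is assumed, with sphericity.
- Group effect: λ = f²·N·m/(1 + (m − 1)ρ) = 3.675/2.5 = 1.47 at ρ = 0.5, and 3.675/3.1 = 1.19 at ρ = 0.7, with 1 and 28 df. Power is about 0.22 and 0.18.
- Interaction: λ = f²·N·m/(1 − ρ) = 7.35 and 12.25, with 3 and 84 df. Power is about 0.59 and 0.83.

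**The case against.** The strongest reply is that the parenthesis is shorthand. The sentence stands under the primary heading and uses the protocol's term for a learning outcome. It does not say mean or average, as H4 does, and it names settings, as a description of the data source might. Both H3 measures can be computed from the same step record: the proportion counts steps by their change from baseline, and subtracting a fixed baseline value leaves a participant's variability unchanged. H1's list of learning outcomes opens as examples only, so the absence of FPA change there proves little.

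The point about H1 stands, and so does the shared data source. They do not rescue the sentence. H2's list and the protocol's list of learning measures are not given as examples, and both omit FPA change. A model needs a response variable, and the one stated is neither a spread nor a threshold proportion.

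A second reply is that the protocol already describes a 2 × 4 ANOVA on retention tests and sized its interaction. That is true, and the group effect has much less power. But H3 is about the level of variability and of the proportion in each arm, which the group effect tests. The sample-size paragraph also names no dependent variable measured in both arms: its primary outcome applies to SMOD only.

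Third, the step figures are hypothetical. They show that the summaries can part, not that they will in this trial.

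Finally, the protocol's Study Design section promises that "Both within-group and between-group comparisons will be made to identify differences in learning, difficulty, biomechanical, and clinical outcomes". This states the intention to compare learning, but supplies no outcome, model or time point.

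**Conclusion.** The concern holds. As written, the SAP's primary between-group model tests the variable of secondary H4, and neither outcome of primary H3 has a stated between-group analysis. This follows from the text and depends on no calculation.

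The illustration (gaps of 2 to 26 points in the step proportion for the same 2° difference in mean change) rests on assumed means, SDs and normality. It shows only that FPA change is no proxy.

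The mismatch should be fixed, but it is not a failed design. H3's outcomes are stated in the protocol and measured in both arms, data processing is blinded, the statistician is independent, the primary outcome (performance error in SMOD) is untouched, and the trial calls itself exploratory.

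**What to change.** In the SAP's Primary Hypotheses section:
- Name FPA variability and the proportion of steps beyond 7° as the dependent variables of the two-way mixed ANOVA, one model each.
- Make the group effect the test of H3, and report the group × time interaction alongside.
- State the settings and time points. H1 and H2 already use week 1 to week 6 in practice sessions, learning assessments and daily walking; the sample-size paragraph uses immediate and delayed retention at week 1 and follow-up. Say which apply to H3.

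Keep the mixed ANOVA of FPA change from baseline, but list it under secondary H4, so that H4 still has a stated model.

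Add a reporting rule: where the protocol expects the arms to be alike (the step proportion in H3, the change scores in H6), give the group difference with its 95% CI, and do not read p > 0.05 as evidence of similarity.

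The cost is SAP wording and one or two extra models on data already planned in both arms. Low precision should be acknowledged. With half-widths of about 0.75 SD at 15 per arm and 0.68 SD at 18, a claim of no difference will probably not be supportable. Power for the group effect is about 0.18 to 0.22 at the protocol's f and N = 30, under the assumed correlations of 0.5 to 0.7.

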The gait screen will be performed using motion capture to measure self-selected FPA, joint angles, and joint moments during over-ground walking. Fifty-two retroreflective markers will be placed on the skin over boney landmarks and 14-high speed cameras (sample rate = 100 Hz) will track the positions of these markers in three dimensions. Additionally, two floor-mounted force platforms (sample rate = 2000 Hz) will measure ground reaction forces during walking. Natural walking trials across the 10m instrumented walkway will be performed first (one length equals one walking trial), followed by toe-in and toe-out walking. The latter will be guided verbally such that several walking passes are completed at a range of FPA magnitudes (small toe-in/out, medium toe-in/out, and large toe-in/out). The specific amount of change in FPA is not relevant, as long as a range of FPA magnitudes are recorded over the collected walking trials. These data will be used to determine whether the participant is a responder to FPA modification, and which direction (toe-in or toe-out) elicits the greatest response. The threshold of a 5% reduction in the knee adduction moment impulse (area under the knee adduction moment – time curve) with a 10° change in FPA will be used to determine response. For recruitment purposes, those who respond to either toe-in or toe-out ($\geq 5\%$ reduction with a 10° change in FPA) will be provided this FPA modification. For those who elicit response to both, the modification (toe-in or toe-out) with the greatest reduction per 10° of change in FPA will be used in the intervention. This cutoff value is conservative, allowing for some regression in response while still maintaining overall reduced KAM impulse. A 5% threshold was chosen as the average reduction in KAM impulse after a 16 week toe-out modification program was 4.7% [5]. These methods of screening for response to FPA change and personalizing the direction of FPA change were shown to improve biomechanical outcomes relative to a non-personalized approach [6, 7].

Baseline and follow-up data collection

An identical baseline and follow-up gait assessment, separated by seven weeks, will be conducted in the laboratory, and using both optical-motion capture and the sensorized shoe system. These assessments will include questionnaires, a timed stair climb, and gait analysis.

A) Patient reported outcomes and physical function

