Questionnaires will be administered which will include an 11-point numerical rating scale (NRS) depicting average knee pain over the previous week where 0 = “no pain”, 10 = “worst pain imaginable”, the Knee Injury and Osteoarthritis Outcome Score (KOOS) [8], and the Pain Catastrophizing Scale [9]. Medical history, anthropometrics (height, body mass etc.), age, and symptom duration will also be recorded by the assessor. The timed stair climb (a measure of physical function) will be performed on a 12-stair flight. Participants will be instructed to “climb as quickly, but safely as possible” [10]. Two repetitions will be performed, and the fastest time will be used.

B) Gait analysis

A total of 52 reflective markers (45 lower limbs; 7 upper limbs) will be affixed to the skin bilaterally over key anatomical landmarks as is standard in our laboratory [11]. Fourteen high-

speed cameras (sample rate = 100 Hz) will track the positions of these markers and two floor-embedded force platforms (sample rate = 2000 Hz) will measure ground reaction forces. Five passes along a 10m instrumented walkway will be performed barefoot and then shod. Walking speed at the baseline assessment will be measured using two timing gates placed at a known distance along the walkway. At follow-up, participants will first complete five walking passes at a self-selected speed and then be constrained to walk within $\pm 5\%$ of their baseline walking speed, due to the impact of walking speed on joint moments. After over-ground walking, a 5-minute treadmill walk will be performed while wearing a pair of sensorized shoes (details included below). This will provide a controlled measurement of FPA from the sensorized shoe for comparison with FPA measured at each practice session and during daily at-home walking.

A 1-minute dual-task assessment will be performed immediately after the 5-minute treadmill walking trial, according to established methods [12]. Briefly, a single letter or category will be provided at the start of the 1-minute period. The instructions will be to continue walking naturally while simultaneously dictating as many words as possible (word-list generation) that start with the letter or belong to the category. The number of correct words dictated will be recorded.

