Stair ascent and descent will be performed while wearing the sensorized shoes. This will take place at a building nearby the laboratory (5-minute walk) because of the availability of continuous linear sets of stairs for multiple flights. This allows the use of the sensorized shoe for measuring FPA during stair ascent and descent. These FPA data will be compared with transfer test data (details included below) examined at several points throughout the intervention. These same shoes will be provided to the participant to measure real-world FPA during at-home and community walking.

Sensorized shoes

A custom inertial sensor consisting of a 3-axis accelerometer (signal range: $\pm 4g$), gyroscope ($\pm 500^\circ/s$), and magnetometer ($\pm 1200\mu T$), sampling data at 100 Hz will be embedded in the sole of the shoe. A previously published custom sensor fusion algorithm [13], programmed into a microcontroller, calculates the FPA in real time and stores it on a microSD card for later extraction. The sensorized shoe design and algorithm has been validated during treadmill [14] and over-ground walking [15] with excellent validity and reliability (absolute error = 1.7° and intraclass correlation coefficients > 0.9).

Randomization

Once deemed eligible and baseline data collection is complete, each participant will be randomized to either the SMOD or AMAC group. Randomization will be performed using an *a priori* block-stratified approach based on sex and KL grade. A predetermined randomization matrix will be computed [16] by a team member not involved in testing or the intervention. Group allocations will be stored in opaque envelopes, which will be opened in a sequential manner after baseline testing and before the first practice session. The group allocation will be communicated to the study trainer via email.

Gait modification intervention

Both groups will attend six practice sessions conducted weekly, which will last approximately 1 hour each. Walking practice will be conducted on a treadmill with a full-length mirror placed

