During each practice session, participants will be asked to rate their knee pain at the beginning, middle, and end of the session using an 11-point numerical rating scale (0 = “no pain” and 10 = “worst pain imaginable”). At the end of the sessions, they will be asked to rate the difficulty in achieving their FPA modification during that practice period using an 11-point numerical rating scale (0 = “not difficult” and 10 = “most difficult/unable to perform”).

An instructional booklet will be provided which outlines details of how to care for and use the sensorized shoes while at home and in the community. Participants will track daily walking volume, walking times on each day, daily knee pain using an NRS (e.g. overall pain, pain during walking), non-walking exercise activities, and any adverse events related to their knees or walking. Additionally, an 11-point numerical rating scale will be used to report weekly confidence in how accurately the FPA modification was performed (0 = “no confidence at all/unable to perform” and 10 = “completely confident”) and difficulty in performing the modification (0 = “not difficulty” and 10 = “most difficult/unable to perform”). A minimum of 10-minutes of daily walking will be requested to ensure enough data for the analysis.

Data processing and analysis

Marker-based motion capture data (as collected during the baseline and follow-up assessments) will be processed using commercially available software and using standard techniques our research group has established [5, 11, 19, 20]. Sensorized shoe data captured during the baseline and follow-up gait assessment, practice sessions, and at-home or community walking will be processed using custom MATLAB scripts. A trained research assistant, blinded to group allocation, will perform all data processing and analysis.

References

- [3] Richards R, van der Esch M, van den Noort JC, Harlaar J. The learning process of gait retraining using real-time feedback in patients with medial knee osteoarthritis. *Gait Posture.* 2018;62:1-6.

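### Difficulty is to be analysed as a baseline-adjusted change, but every planned rating comes after allocation and H4 predicts a difference in level

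*SAP*

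**What the plan says.** The SAP (Secondary Hypotheses) groups difficulty with the knee moments, pain and KOOS scores: "difficulty (difficulty of performing the FPA modification) change scores will be examined using an analysis of covariance (ANCOVA"), with "baseline outcome values included as covariates", together with any demographic variable that differs significantly at baseline. It gives no other analysis of difficulty and no start or end point for the change.

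The protocol plans two difficulty ratings, both on a 0–10 scale and both described under Gait modification intervention:

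- After practice: "At the end of the sessions, they will be asked to rate the difficulty in achieving their FPA modification during that practice period".
- In the weekly home report, alongside confidence: "and difficulty in performing the modification (0 = “not difficulty” and 10 = “most difficult/unable to perform".

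For the baseline and follow-up laboratory visits the protocol says: "These assessments will include questionnaires, a timed stair climb, and gait analysis". Under Patient reported outcomes and physical function it says: "Questionnaires will be administered which will include an 11-point numerical rating scale (NRS) depicting average knee pain over the previous week". The other named questionnaires are the KOOS and the Pain Catastrophizing Scale. Allocation (Randomization) is by envelopes "which will be opened in a sequential manner after baseline testing and before the first practice session".

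H4 (protocol, Secondary Hypotheses) predicts that AMAC participants will find their modification less difficult than SMOD participants do. H6, which concerns change from baseline to follow-up, covers biomechanical and clinical outcomes and does not name difficulty.

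**The concern.** The model set down for difficulty needs a pre-randomisation value that the trial does not plan to collect. It also estimates a difference in change where H4 predicts a difference in level.

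The statistician would have to settle three things the SAP leaves open: which rating, which start value, and which end value. If week 1 is the start value, adjusting for it conditions on something the allocation has already affected and removes part of any gap present by then. If AMAC is easier from the first session and stays so, H4 is true, yet the adjusted difference is shrunken and the unadjusted change is zero. H4 sets lower difficulty against the smaller change in foot progression angle it expects in AMAC, so a distorted answer here would affect how the two ways of delivering the modification are compared.

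**Working it through.** **Which ratings exist, against the time of allocation**

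| Occasion | Difficulty rating planned? | Relative to allocation |
|---|---|---|
| Gait screen | None listed | Before |
| Baseline visit | None listed | Before |
| Practice sessions, end of session | Yes | After |
| Weekly home report | Yes | After |
| Follow-up visit | None listed | After |

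No row gives a rating before allocation. Both ratings ask about performing the modification, which participants start practising only after baseline testing. A baseline-to-follow-up change therefore cannot be formed.

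**Can week 1 stand in?** The protocol uses a week-1 reference for the learning outcomes (H1, H2) and for the primary outcome (Participants). The SAP does not extend it to difficulty. By the end of session 1, SMOD has practised to a 15° target marked by tape on the mirror. For the other arm, "The AMAC group will be instructed to increase their FPA by “as much as is comfortable", without tape. The session-1 rating therefore already reflects allocation.

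**What each analysis estimates.** Let g1 and g6 be the gaps (SMOD minus AMAC, positive favouring H4) at sessions 1 and 6, with equal variances and correlation ρ.

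- Unadjusted change: g6 − g1.
- ANCOVA of the change on group and session 1: the within-group slope of the change on session 1 is ρ − 1, so the adjusted difference is (g6 − g1) − (ρ − 1)·g1 = g6 − ρ·g1.
- Final-session level: g6.
- Six-session mean: the average gap, with SD √((1 + 5ρ)/6) for participant means under compound symmetry.

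**Illustration.** The documents give no SD, gap, correlation or time course for difficulty, so all of these are assumed: SD 1, normal ratings, compound symmetry, a linear gap, and ρ = 0.4 / 0.6 / 0.8. There are 15 per group (the protocol's required total of 30, divided by 2), with two-sided alpha 0.05. Each cell used 20,000 simulated trials. Power is the chance of a significant result favouring AMAC.

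| Gap, session 1 to 6 (SD) | ANCOVA estimate, g6 − ρ·g1 | ANCOVA power | Unadjusted change power | Final-session power | Six-session mean power |
|---|---|---|---|---|---|
| (a) 1.0 to 1.0 | 0.60 / 0.40 / 0.20 | 0.33 / 0.22 / 0.12 | 0.025 | 0.75 | 0.96 / 0.90 / 0.83 |
| (b) 0.5 to 0.5 | 0.30 / 0.20 / 0.10 | 0.13 / 0.09 / 0.06 | 0.025 | 0.26 | 0.46 / 0.37 / 0.31 |
| (c) 0.5 to 1.0 | 0.80 / 0.70 / 0.60 | 0.59 / 0.60 / 0.71 | 0.23 / 0.32 / 0.55 | 0.75 | 0.80 / 0.68 / 0.58 |
| (d) 1.0 to 0.5 | 0.10 / −0.10 / −0.30 | 0.05 / 0.01 / 0.002 | not tabulated; estimate −0.50 | 0.26 | 0.80 / 0.68 / 0.58 |
| (e) 0 to 1.0 | 1.00 / 1.00 / 1.00 | 0.80 / 0.90 / 0.99 | 0.68 / 0.84 / 0.99 | 0.75 | 0.46 / 0.37 / 0.31 |

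In (d) the adjusted difference is 0.5 − ρ × 1.0, which turns negative once ρ exceeds 0.5. The ANCOVA is then significant in the wrong direction in 0.01 / 0.05 / 0.21 of trials, and the unadjusted change in 0.23 / 0.32 / 0.55.

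**Checks.** The simulated mean ANCOVA differences agree with g6 − ρ·g1 to within 0.01 SD in all 15 cells. Noncentral-t power for the unadjusted change, the final session and the mean agrees with simulation to within 0.01.

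**The case against.** The strongest reply is that week 1 is plainly the working reference in a learning study, and that asking whether difficulty falls faster in one arm is reasonable. On that reading the analysis can be run, and the defects are an unstated reference point and a missing test of level. This stands as a description of a possible secondary question. It does not give H4 a test, and it does not make a post-allocation rating a baseline.

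Other points have some force:

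- The lists of baseline assessments are not worded as exhaustive. No earlier difficulty rating appears anywhere in either document, however.
- Every magnitude is assumed, and the ratings are bounded integers, not normal values. The SAP falls back on an unnamed non-parametric test if normality fails, so the ANCOVA may not be the final test. The figures show direction and range only. The fallback does not help if it is applied to the same change score.
- The unadjusted change is not what the SAP specifies, so its figures add context and should not drive the judgement.
- The open choices need not be made with sight of the results. The protocol has a blinded assistant processing and analysing data, and the SAP has an independent statistician. This lowers the risk of a data-driven choice but does not supply the missing definition.
- The SAP will report means and SDs for each outcome, so difficulty levels would be described, though not formally tested.
- H4 names no time point, so the choice of level summary is a judgement.

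**Conclusion.** The concern holds. As written, the difficulty analysis has no baseline value to use. With week 1 substituted, it conditions on an outcome of allocation and answers a different question from H4. That conclusion comes from the text and rests on no assumed number.

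The size for this trial cannot be determined from the documents. Under the assumptions above, the consequence runs from no loss (no gap at session 1) to a reversed sign (a gap that halves, with ρ above 0.5). A level comparison is not uniformly more powerful: the six-session mean does worse than the ANCOVA in (e), and in (c) at ρ = 0.8. The reason to change is the match to H4 and the avoidance of a post-allocation covariate, not power.

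The scope is narrow: the difficulty part of one secondary hypothesis in a trial titled exploratory. The primary outcome, the sample size and the foot-angle part of H4 are untouched. The plan should be corrected before group results are seen.

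**What to change.** Take difficulty out of the change-score ANCOVA. Name the rating that tests H4 and one summary of its level, and use no post-allocation difficulty rating as a covariate. Possible SAP wording:

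> Difficulty (H4) will be compared between groups using the end-of-session rating from practice sessions 1–6, in a mixed model with group, week (categorical), group-by-week and a participant random intercept. The test of H4 is the group difference averaged over the six sessions. The weekly home rating will be analysed in the same way as supportive evidence.

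The final-session level would also fit H4, but one of the two must be chosen in advance. The SAP should also say whether its rule on demographic covariates applies to this model; the wording above leaves them out.

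The cost is one or two sentences and no new data. The downside is lower power if the gap appears only late: in scenario (e) the six-session mean has 0.46 / 0.37 / 0.31 against 0.80 / 0.90 / 0.99 for the week-1-adjusted analysis. Choosing the final session raises that to 0.75 but gives up power when the gap is constant or narrowing.
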